### **DuraDerm® Group (IDENTICAL CARE AS DESCRIBED ABOVE + Step 3)**

Step 3:      Apply DuraDerm® with Q-tip on clean dry wound around (extending approximately one inch around pin site) and on the pin. DuraDerm® will be applied daily while in the hospital and then at a minimum of at least three times a week until pin removal.

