## **Pin Track Care Regimen**

### **Control and DuraDerm® Groups**

All pins and wire sites will be cleaned daily while hospitalized. Basic pin care will be performed once daily by hospital nursing staff prior to discharge. Following discharge from the hospital, the pin care protocol will be continued by research participant's caregiver.

Ideally, pin sites are cleaned when the surrounding skin and gauze are soft. This should make removal of gauze and cleaning of pins less painful. The purpose of the cleaning is to prevent the skin from attaching to the pins and wires and to decrease the chance of infection, as well as, inspect the area for any signs of infection.

Research participants will be instructed to notify the Principal Investigator if they observe any signs or symptoms of infection. These include redness around pin site, discharge, tenderness in the soft tissue, loosening of the pin, nausea, vomiting, fever or chills.

Research participants will be instructed that the approach to pin care should occur in a step-wise fashion. If Step 1 is effective there is no need for further debris removal and research participants will be instructed conclude the care protocol (Control Group) or proceed to Step 3 (DuraDerm® group). Basically, if Step 1 removes all debris, Steps 2 is not necessary. It is not uncommon for all of Steps 1 and 2 to be needed to completely remove debris.

Step 1:      Brush the pin sites with saline using an ordinary soft toothbrush or gauze with sterile gloves

Step 2:      If following Step 1, debris remains, use forceps (tweezers) to gently remove debris.

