**DuraDerm® should be reapplied at the end of each Pin Care Cleaning Regimen.**

**See Attachment – Schedule of Events**

### **Data Analysis and Data Monitoring**

This is a prospective observational case series study to measure the potential reduction in pin track infection rate among research participants undergoing Deformity Correction and Traumatic Provisional Fixation.

Data will be collected by clinical staff under supervisor of the Principal Investigator. Data collected is primarily categorical and will be analyzed using tabulations (tables of frequencies), visual displays (histograms), and chi-square or Fisher exact tests to measure variable independence (e.g., infection rate based on age, number of pins/research participants, etc.).

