### **Protection Against Risk**

All research participants will be monitored for potential redness or irritation at the pin track sites, and if any occurs, discontinuation of application may be warranted if it is believed to be a result of a reaction to the product. Any significant adverse event will be reported to the FDA utilizing FDA Medwatch Form 3500.

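### Step 3 has no instruction to hold DuraDerm, pending review, at a clean, dry pin site that is red, tender or loose, and its margin is below the Protocol's own product description

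*Protocol*

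**What the plan says.** In the Protocol, the DuraDerm group gets the control group's cleaning plus Step 3: "Apply DuraDerm® with Q-tip on clean dry wound around (extending approximately one inch around pin site) and on the pin". The schedule is "DuraDerm® will be applied daily while in the hospital and then at a minimum of at least three times a week until pin removal", and the line after Step 3 adds "DuraDerm® should be reapplied at the end of each Pin Care Cleaning Regimen". Neither sentence states an exception.

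The Pin Track Care Regimen says who does this at home: "Following discharge from the hospital, the pin care protocol will be continued by research participant's caregiver". It makes inspection for infection part of each cleaning and then says "Research participants will be instructed to notify the Principal Investigator if they observe any signs or symptoms of infection". Of the signs: "These include redness around pin site, discharge, tenderness in the soft tissue, loosening of the pin", followed by systemic symptoms. No other action is attached to them.

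The one stopping provision is in Protection Against Risk. It begins "All research participants will be monitored for potential redness or irritation at the pin track sites" and continues that, if this occurs, "discontinuation of application may be warranted if it is believed to be a result of a reaction to the product".

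The product description in the Background lists infected wounds among those for which DuraDerm is not meant. It also sets the coating margin at a minimum of 1.25 inches past the wound edge.

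**The concern.** The Protocol names the signs of infection and names infected wounds as outside the product's use, but it never connects the two at the step where the product goes on. A site can be red, tender or loose while still clean and dry. Such a site meets Step 3's only condition, and the person deciding is usually a lay caregiver who has been told to report and has not been told to wait.

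Two things are at stake. One is safety: a film-forming product may be put on a wound that the Protocol's own description excludes. The other is a clean record of the outcome. Redness appears both as a sign of infection and as a possible reaction to the product, and the supplied text gives no rule for telling them apart. Only a treated site can be put down to the product.

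Separately, Step 3 asks for less coverage than the product description and gives no reason.

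**Working it through.** The plan gives no figure on this point, so there is none to reproduce. The main check sets the instructions side by side.

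**1. What the text tells a caregiver to do, sign by sign**

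| Sign after cleaning | Step 3 condition (clean, dry) | Pin Track Care Regimen | Protection Against Risk | Written result before review |
|---|---|---|---|---|
| Redness | Met | Notify | Stopping possible if believed a product reaction | Reapply, unless judged a reaction |
| Tenderness | Met | Notify | Not named | Reapply |
| Pin loosening | Met | Notify | Not named | Reapply |
| Discharge | Arguably not met | Notify | Not named | Arguably withheld already |

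The Inclusion Criteria ask for stable pins and the Exclusion Criteria for a clean, dry wound. These govern entry to the study and do not govern later applications. The gap is therefore the first three rows, between notification and the investigator's review.

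**2. How often the product would be applied**

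Inputs: at least 3 applications a week after discharge (Step 3); up to 6 to 8 weeks after discharge (Criteria for Research Participant Selection); about 60 DuraDerm sites.

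- Per week of waiting for review: 3 at the minimum, or 7 if cleaning is daily at home (an assumption; no home cleaning frequency is stated apart from Step 3's minimum).
- Whole period, per site: 3 × 6 = 18 to 3 × 8 = 24. If daily: 7 × 6 = 42 to 7 × 8 = 56.
- Over 60 sites at the minimum frequency: 60 × 18 = 1,080 to 60 × 24 = 1,440.

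The whole-period counts combine a minimum frequency with the longest planned period, which itself runs to a visit after pin removal. They are not a bound in either direction. They count all applications, not those at sites with signs. How many sites had signs, and how long review took, is not in the documents.

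**3. Margin**

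Inputs: about 1 inch around the pin site (Step 3); at least 1.25 inches past the wound edge (Background).

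- Shortfall: 1.25 − 1.00 = 0.25 inch; 0.25 / 1.25 = 20%.
- Area of skin covered, with margin m and wound radius r: π[(m + r)² − r²]. For r = 0 the ratio is 1.00² / 1.25² = 0.64.
- The documents give no wound radius. Assuming r = 0.03 inch, the ratio is 3.330 / 5.144 = 0.647. Assuming r = 0.125 inch, it is 3.927 / 5.890 = 0.667.

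Step 3 thus covers roughly one third less skin than the described minimum.

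**The case against.** The strongest reply is that the gap is narrow and largely covered. Each cleaning includes inspection, signs must be reported, Step 3 requires a clean, dry wound, and redness or irritation can lead to stopping. The Protocol also records that training in the product was given and documented, though not to whom or with what content. The Schedule of Events, consent form and Data Collection Sheet are referred to but were not available, and caregiver instructions could well be there. All of this stands, and it limits the point to the interval before review and makes the fix conditional. It does not supply the missing instruction: reporting is not withholding, and the stopping provision is discretionary and tied to a believed reaction.

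On the margin, it is fair that Step 3 says approximately and measures from the pin site, while the Background measures from the wound edge. That softens the difference but does not explain it.

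A reader might infer more than the documents support:

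- **That reactions were taken out of the DuraDerm infection count.** Protection Against Risk deals with stopping application and says nothing about how a site is counted.
- **That 0 of 60 infected DuraDerm sites (SAP, Table 2) shows the gap never arose.** The gap is defined by signs, and the report counts infections only.
- **That literature or control-group infection rates measure the number of sites affected.** They count all infected sites, not clean, dry sites with signs.
- **That the minimal-risk statement fails because pin sites are outside the described indication.** Potential Risk addresses pin-site use directly, and Methods and Procedures openly calls it experimental.

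**Conclusion.** The point holds as a gap in the written procedure. On the supplied text, DuraDerm would be reapplied before review at a clean, dry site that is red, tender or loose, although the Protocol treats those as signs of infection and says the product is not meant for infected wounds. The exposure is at least 3 applications per site for each week of waiting. The number of sites concerned, and any effect on the infection counts, cannot be known from the documents.

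The margin is 0.25 inch (20%) below the described minimum, without a reason and with no clinical consequence shown.

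No sample size, significance level, test or reported result changes. The conclusion assumes that the unavailable attachments contain no hold instruction; if they do, the first part falls away.

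**What to change.** For further enrolment or a repeat study, and unless the attachments already cover it:

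- **(a) Hold.** Add to Step 3: *Withhold DuraDerm at any pin site with redness, discharge, tenderness or pin loosening until the investigator has reviewed it; do not resume at an infected site; continue to follow and analyse the site in its assigned group.* Judge infection by the same sign-based criteria in both groups, without regard to a suspected product reaction. A rule that counted unclear reactions as infections would not do, because it could operate in the DuraDerm group only.
- **(b) Margin.** Change Step 3 to at least one and a quarter inches beyond the wound edge.

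The SAP document is a final report dated December 23, 2019, so (a) and (b) cannot affect these 12 patients. For that report, add a sentence giving the number of sites with redness in each arm and the number of DuraDerm sites where application stopped, or say that these were not recorded.

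The cost is two edits to Step 3, matching caregiver instructions, a short statement of infection criteria common to both groups, and one sentence in the report. The downside is that some treated sites will miss applications while awaiting review.

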**DuraDerm® should be reapplied at the end of each Pin Care Cleaning Regimen.**

**See Attachment – Schedule of Events**

### **Data Analysis and Data Monitoring**

This is a prospective observational case series study to measure the potential reduction in pin track infection rate among research participants undergoing Deformity Correction and Traumatic Provisional Fixation.

Data will be collected by clinical staff under supervisor of the Principal Investigator. Data collected is primarily categorical and will be analyzed using tabulations (tables of frequencies), visual displays (histograms), and chi-square or Fisher exact tests to measure variable independence (e.g., infection rate based on age, number of pins/research participants, etc.).

### **Data Storage and Confidentiality**

Data will be stored on Principle Investigator's computer which is secured by password protection. A hard copy backup will also be kept and be stored in a locked cabinet or office with limited access. Confidentiality will be maintained by assigning each research participant a unique research participant identifier. Research participant identifier will consist of research participant's initials and date of birth. Raw data will not be shared with anyone. Tabulated data with confidential research participant identifiers will only be shared with study coordinator and statistician.

### **Risk/Benefit Assessment**

#### **Risk Category**

This research study presents minimal risk to the research participant. DuraDerm® has been used by over 3,000 individuals without any reported serious side effects

#### **Potential Risk**

The most common side effect of DuraDerm® is momentary stinging upon application. Intentional inhalation of the contents may be harmful or fatal. The product should be used with adequate ventilation. DuraDerm® should be kept away from children and not used near the eyes, mouth, or nose. The solution may be damaging to clothes or finished surfaces. If ingested, obtain medical assistance immediately. If used as directed, the probability of any potential risk is minimal. Since this study is being conducted on

extremity pin tracks, the application will be of significant distance from the eyes, mouth or nose. The only foreseen risk from the application of DuraDerm® on pin track sites is momentary stinging and this is not a consistent risk.

### **Protection Against Risk**

All research participants will be monitored for potential redness or irritation at the pin track sites, and if any occurs, discontinuation of application may be warranted if it is believed to be a result of a reaction to the product. Any significant adverse event will be reported to the FDA utilizing FDA Medwatch Form 3500.

### **Potential Benefit to the Research participants**

Since the infection rate of pin track research participants is approximately 27%, and initial information provided by the principle investigator indicates a much lower pin track infection rate, the benefit of reduced infection appears to significant.

### **Alternatives to Participation**

Should a research participant elect not to participate in the study, they will receive standard pin track site care as described for the control group.

### **Research participant Identification, Recruitment and Consent Form**

### **Method of Research Participant Identification, Recruitment and Consent/Assent**

Research participants identified for the study will be those undergoing Deformity Correction and Traumatic Provisional Fixation who are under the care of the Primary Investigator. These research participants have a number of pins placed to ensure this required rigid fixation. The number of external fixation pins averages approximately ten per research participant. Research participants seen by the Primary Investigator who will be undergoing deformity correction or traumatic provisional fixation, will be invited to take part in this research study. No recruitment of the Principal Investigator's own students, employees, or family members will be allowed. Research participants who do not wish to participate in this randomized study will be provided the standard pin track care protocol this investigator utilizes for his research participants and will not have the opportunity to receive DuraDerm®.

### **Process of Consent**

The Primary investigator and other key personnel on the study (fellow, nursing staff, intake coordinator and others) will be authorized to obtain consent from potential research participants for inclusion in the study. The process will be structured to present to the research participants the option to take part in this research that is intended to provide more conclusive information on the ability of DuraDerm®, a new liquid polymer

technology to reduce pin track infections. The potential research participants will be provided the consent form and this information will be explained to them. It will be made clear that participation in the study is completely voluntary and if they do not choose to take part in the study, they will receive the usual pin track standard of care provided by the Primary Investigator. The Primary Investigator or authorized team member will be responsible for signing as witness of consent being given.

### **Research Participant Capacity**

All research participants will have the capacity to provide informed consent. If a research participant presenting to the Primary Investigator's practice, is not able to provide informed consent, they will not be presented the opportunity to take part in the study.

### **Research Participant/Representative Comprehension**

If a research participant has been determined to be eligible for study participation based on the inclusion/exclusion criteria, they will be provided with the consent form and the information within the consent form will be discussed. Only those research participants indicating they understand the risks and benefits of receiving DuraDerm® as part of their pin track care protocol in the study and stating clearly that they would like to voluntarily participate, will be given the opportunity to take part in the study.

### **Debriefing Procedures**

No information will be purposely withheld from the study research participants.

### **Consent Form**

See attached.

### **Documentation of Consent**

Consent will be documented on an individual consent for each research participant. These forms will be kept in a secure file cabinet in the Principal Investigator's office.

### **Cost to Research Participants**

Research participants in this study will incur no additional costs for participation in the study. All DuraDerm® will be provided at no cost to the research participants in the DuraDerm® treatment group. No additional charges other than those normally occurring under the standard pin track care protocol will occur. All DuraDerm® will be provided by Prevent-Plus, LLC, the patent holder of DuraDerm®.

### **Payment for Participation**

No payment or any other type of reimbursement will be provided to the research participants in this study.

## Final Report for DuraDerm Data Analysis

December 23, 2019

Here are the results of the analysis of your DuraDerm data. You are interested in determining whether patients undergoing orthopedic reconstructive or repair surgery for deformity correction or trauma who have an external fixation held in place by metal pins experience lower infection rates when DuraDerm is applied to the pin site than patients who receive no DuraDerm (Control). The data set consists of twelve patients who each had, on average, ten pins holding the external fixation in place. Six of the patients were randomly selected to receive a DuraDerm application while the other six patients received no DuraDerm. Both groups of patients received standard pin track care. You would like to answer this question from both the patient-level perspective and the pin-level perspective. A level of significance of  $\alpha = 0.05$  was used throughout. SAS version 9.4 (SAS Institute, Inc., Cary, NC) was used for all analyses. Descriptive statistics for the patient demographics are provided in the appendix.

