5. There is no consistency in reporting infection rate (per patient vs per individual pin site). This creates difficulty in studying incidence, comparing studies, or conducting an accurate meta-analysis.

Research participants eligible for the study will be those undergoing Deformity Correction and Traumatic Provisional Fixation. These research participants have a number of pins placed to ensure this required rigid fixation. The number of external fixation pins averages approximately ten per research participant.

DuraDerm® is a 510K FDA cleared medical device indicated for providing a covering over minor wounds and scrapes that are clean and dry. The microbicidal liquid solution consists of organic polymer dissolved in methylene chloride organic solvent. The unique formulation eradicates any organisms (bacteria, fungi, viruses) it comes in contact with. This is a result of the methylene chloride's activity against an infinite number of organisms. The methylene chloride evaporates leaving a clear, elastomeric, non-odorous film for covering minor wounds. The film protects the wound against entry of water, dirt, and germs. The film is elastomeric and protects in difficult regions where flexing, bending and creasing skin occurs. The clear film forms in less than a minute. Application is commonly accomplished using a cotton tip applicator. The liquid is applied on and around the wound extending at least an inch and a quarter beyond the edges of the wound. Momentary stinging may occur upon initial application. The film commonly remains intact for one to three days or longer depending on exposure to rubbing, flexing, or soap and water. This film is resistant to degradation by water alone, but can be easily removed with the combination of soap and water or it can be gently peeled off starting at the outer edges. DuraDerm® is for external use only. DuraDerm® is not intended for use on deep or infected wounds or puncture wounds, or for use near the eyes, mouth, or nose. Intentional inhaling of the contents may be harmful or fatal. The bottle should be tightly capped after each use to prevent evaporation of the solvent.

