### 1 Patient-level Results

For the patient-level portion the response variable is whether the patient developed an infection (i.e. had at least one infected pin). The results are given below in Table 1. The top number in each cell is the number of patients in the given category, and the bottom number is the row percentage. For example, two of the patients in the Control group experienced an infection. This accounts for 33.33% of the patients in the Control group.

A chi-square test is usually appropriate for this type of data, however the chi-square test assumes the expected frequency in each cell is at least 5. This does not hold true for this data set, so Fisher's exact test was run instead. Fisher's exact test has no such expected frequency assumption. The two variables were Group (DuraDerm or Control) and Infection (Yes or No). Based on a  $p$ -value of 0.45, there is not sufficient evidence to suggest there is a significant association between Group and Infection.

Table 1: Patient infection outcomes

Group	Infection		
	Yes	No	Total
DuraDerm	0	6	6
	0%	100%	
Control	2	4	6
	33%	67%	
Total	2	10	12

Table 2: Pin infection outcomes

Group	Infection		
	Yes	No	Total
DuraDerm	0	60	60
	0%	100%	
Control	14	46	60
	23%	77%	
Total	14	106	120

Note that an *a priori* power analysis indicated that the minimum sample size required to achieve 80% power was 33 patients per group. Due to a lack of 66 available patients, this portion of the analysis is severely under-powered. However, from a descriptive standpoint the results were in line with the values that went into the power analysis. So if the observed trend continued with the appropriate sample size, it would become statistically significant.

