## 2 Pin-level Results

These studies are reported in the literature at both the patient-level and the pin-level. After consultation with your surgeon it was determined that there is consensus in the orthopedic surgical community that the pins can be treated as independent. Therefore, for the pin-level portion of the analysis the response variable is whether the individual pin site became infected. The results are given above in Table 2.

For this portion of the analysis the chi-square test is appropriate because all of the expected counts are at least five. Do not confuse expected counts with observed counts. The observed count of infections for the DuraDerm group is zero, however the expected count is the column total multiplied by the row total and divided by the total sample size. So for this cell the expected count

would be  $(14 * 60 / 120) = 7$ .

The same two variables were used (Group and Infection), except now they refer to the individual pins instead of the patients. Based on a *p*-value of <0.0001, there is strong evidence to suggest there is a significant association between Group and Infection.

One way to quantify this association is in terms of a risk ratio, which is a ratio of the risks of infection for the two groups. The estimated risk ratio for this data set is 0.03. This means that a pin that receives DuraDerm is 0.03 times as likely to become infected as a pin that does not receive DuraDerm. Another way of saying this is the risk of a pin becoming infected is 97% lower for the DuraDerm group compared to the Control group. A 95% confidence interval for the true risk ratio is (0.002, 0.57). So while the observed risk ratio was 0.03, it could feasibly be as high as 0.57.

Let me know if you have any questions about anything contained in this report or related to this research in general. I have enjoyed collaborating with you on this project and hope you consider Wright State University's Statistical Consulting Center for future research.

Sincerely,  
[name]

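### No primary unit of analysis is named, and the only claim of effect rests on a pin-level test that ignores allocation by patient

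*SAP*

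**What the plan says.** The opening section of the report (SAP, Final Report for DuraDerm Data Analysis) sets two analyses of one question side by side: "You would like to answer this question from both the patient-level perspective and the pin-level perspective". It adds "A level of significance of $\alpha = 0.05$ was used throughout", and ranks neither analysis. It also records that six of the twelve patients were randomly selected for DuraDerm, so the patient is the unit of allocation.

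- **SAP section 1, Patient-level Results.** A patient counts as infected with at least one infected pin. Table 1 shows 0/6 on DuraDerm and 2/6 on control. Fisher's exact test gives p=0.45, and the report concludes that "there is not sufficient evidence to suggest there is a significant association between Group and Infection". The section states that "the minimum sample size required to achieve 80% power was 33 patients per group" and describes this part as severely under-powered.
- **SAP section 2, Pin-level Results.** Pins are treated as independent, on the strength of a reported consensus among surgeons. Table 2 shows 0/60 and 14/60. The chi-square p-value is below 0.0001, and the report concludes that "there is strong evidence to suggest there is a significant association between Group and Infection". It adds a risk ratio of 0.03 (95% CI 0.002 to 0.57), restated as a 97% lower risk. No sizing in pins is reported.

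The report then closes without drawing the two results together. The protocol section Data Analysis and Data Monitoring lists tabulations and chi-square or Fisher tests. It names no primary endpoint, unit of analysis, order of testing or rule for results that disagree.

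**The concern.** With no primary unit, a reader can take either section as the trial's answer, and the two answers differ. The pin-level section is the one likely to be quoted, since it carries the only claim of effect. The patient-level section says only that the observed trend would become significant at the required size, which is a conditional extrapolation and not a finding.

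At stake is whether the study is cited as strong evidence for DuraDerm or as an inconclusive comparison of twelve patients. The text as written permits the first, on the analysis with the weaker footing: it does not use the unit that was allocated, and no prior sizing is reported for it.

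**Working it through.** **Inputs.** Table 1: 0/6 v 2/6 patients. Table 2: 0/60 v 14/60 pins. Alpha 0.05 for each test (SAP opening section). Required size 33 per group (SAP section 1). About ten pins per patient (both documents).

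**1. Reproduce the report's figures.**

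- Fisher, patients: with 2 infected among 12, the chance that both are controls is C(6,2)/C(12,2) = 15/66 = 0.227. The mirror image is equally likely, so two-sided p = 30/66 = 0.4545 (stated 0.45).
- Pearson chi-square, pins: 120 × (60 × 14)² / (60 × 60 × 14 × 106) = 15.85, p = 0.00007 (stated <0.0001).
- Risk ratio, adding 0.5 to each cell: 0.5/61 divided by 14.5/61 = 0.034, 95% CI 0.0021 to 0.565 (stated 0.03; 0.002 to 0.57).

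The printed results are arithmetically right.

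**2. Where the infected pins lie.** Table 1 has two infected patients, both controls. Table 2 has 14 infected pins, all control. By the report's own definition of an infected patient, all 14 pins belong to those two people.

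**3. Pin totals with the patient as the unit.** Re-allocate the 12 patients 6:6 in all C(12,6) = 924 ways and compare infected-pin totals. A difference of 14 or more arises only when both infected patients fall in the same group:

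p = 2 × C(10,4)/C(12,6) = 2 × 210/924 = 0.4545.

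This holds however the 14 pins divide between the two patients, and it equals the patient-level p. It assumes that every 6:6 allocation was equally likely.

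**4. A rougher check by design effect.** The split of the 14 pins is not reported. Assume 10 pins per patient and splits from 7/7 to 10/4. The within-control intracluster correlation (ICC) is then 0.61 to 0.79 and the design effect, 1 + 9 × ICC, is 6.5 to 8.1. Dividing 15.85 by it gives 2.43 to 1.97, so p = 0.12 to 0.16. This too is above 0.05.

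**5. Is the problem multiplicity?** Two independent tests at 0.05 would give 1 − 0.95² = 9.75%. But a Bonferroni level of 0.025 leaves the pin test significant (0.00007) and the patient test not (0.4545), so splitting alpha settles nothing. Simulating two identical groups (12 patients, 10 pins each, beta-binomial, pin risk 14/120 = 11.7%), the chance that either test rejects is 5.1% at ICC 0, 16% at 0.1, 32% at 0.3 and 43% at 0.5. Almost all of it comes from the pin test. The inflation comes from ignoring clustering; having two tests adds little.

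**6. What the patient-level test could show.** With 0/6 on DuraDerm, 4/6 infected controls give p = 0.061 and 5/6 give 0.015, so significance needs at least five infected controls. At true risks of 33% and 0%, that has probability 6 × (1/3)⁵ × (2/3) + (1/3)⁶ = 13/729 = 1.8%. The study had 6 of 33 per group, or 18% of the required number.

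**The case against.** **Both levels are disclosed.** The report shows both tables and both p-values, and says that the literature uses both units. That stands: nothing is hidden. Disclosure does not say which result answers the question, however.

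**The choice of patients as primary is not forced.** The protocol's Purpose speaks of a pin track infection rate. Its Background first defines the 27% benchmark at a random pin or wire site and later labels it per participant, and enrolment is stated in patients and in pin sites. This stands, so the documents are ambiguous. The patient is still the better lead, because patients were selected for treatment and the only reported a priori sizing is in patients.

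**A primary named now is post hoc.** This also stands. The report is a final report with results known, and a designation inserted into it or into the protocol would look prespecified when it was not.

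Several stronger readings are tempting, and the documents do not support them:

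- *The analysis sized in advance showed no difference.* It was run at 6 of 33 per group and could hardly reject; p=0.45 is absence of evidence.
- *The two results point in opposite directions.* Both favour DuraDerm. They differ only in significance.
- *The split verdict is a defect wholly apart from the independence assumption.* With whole patients as the unit, both comparisons give 0.4545. Only the failure to name a primary stands on its own.
- *The protocol repeats the fault it finds in the literature* (Background, limitation 5). That complaint concerns inconsistent reporting between studies; reporting both units goes some way to answering it.

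**Conclusion.** The point holds. No primary unit was prespecified in either document, the same question received two conclusions at 0.05, and no overall answer is given. The claim of effect rests wholly on the pin-level test. Its p-value moves from 0.00007 to 0.4545 when whole patients are re-allocated, or to roughly 0.12 to 0.16 by design effect, so the report's significance claim depends on the independence assumption.

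The location of the 14 infected pins and the permutation count follow from Tables 1 and 2, with equally likely 6:6 allocation as the one added assumption. The design-effect and error-rate figures rest on assumed pin counts, splits and correlations and are only indicative. The absence of a pin-level sizing means that none is reported; one may exist outside these documents. The rates behind the 33 per group are not given, so that figure cannot be confirmed.

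The data neither show nor exclude an effect.

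**What to change.** In the opening section of the report:

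1. State that no primary unit of analysis was prespecified in the protocol or the report.
2. Lead with the patient-level comparison, giving the reasons (patients were the unit selected to receive DuraDerm; the only reported a priori sizing is in patients) and saying that this order was chosen after the results were known. Do not write it back into the protocol as if it had been planned.

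In section 2, report pin-level counts descriptively. Withdraw the p<0.0001 claim of strong evidence and the confidence interval that rests on independent pins, or replace them with an analysis that respects the patient as the unit. If the risk ratio stays, label it descriptive.

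Close with one overall conclusion, for example: *Infection occurred in 0 of 6 DuraDerm and 2 of 6 control patients (Fisher p=0.45). The direction favours DuraDerm, but with 6 of the 33 patients per group required the comparison is severely under-powered and inconclusive; it neither shows nor excludes an effect.*

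No new data are needed. The work is rewording, plus one short analysis if the pin-level inference is replaced and not withdrawn. The downside is a less favourable headline.
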